1.3 Secondary Study Endpoints

The secondary objective of this pilot study is to evaluate the safety of daily administration of liraglutide in humans seeking treatment for an OUD.

1) Cardiorespiratory Function

- a. *Blood Pressure*. Change in blood pressure from baseline (Day 1) to: i) the beginning of each study drug dose (Days 2, 8, 14, 20, 26); ii) end of the target drug dose (Day 19 [Day 31 for 5-dose intervention]); and iii) rebound follow-up (Day 21 [Day 33 for 5-dose intervention]).
- b. Heart Rate. Change in heart rate from baseline (Day 1) to: i) the beginning of each study drug dose (Days 2, 8, 14, 20, 26); ii) end of the target drug dose (Day 19, [Day 31 for 5-dose intervention]); and iii) rebound follow-up (Day 21 [Day 33 for 5-dose intervention]).
- c. *Respiration*. Change in respiratory from baseline (Day 1) to: i) the beginning of each study drug dose (Days 2, 8, 14, 20, 26); ii) end of the target drug dose (Day 19 [Day 31 for 5-dose intervention]); and iii) rebound follow-up (Day 21 [Day 33 for 5-dose intervention]).

- 2) **Body Weight** (*kg*). Absolute and percent change in body weight from baseline through the end of rebound follow-up (Daily, from Days 1 to 21 [Days 1-33 for 5-dose intervention]).
- 3) **Glycemic Control.** Glycemic control will be monitored by fasting blood samples for fructosamine and A1c. Fasting blood sample measurements change slowly overtime (i.e., across weeks and months) and therefore will be evaluated only on Days 2 and 19 [and additionally Day 31 for 5-dose intervention] via venipuncture.
- 4) Adverse Events. Frequency of adverse events (AE) and serious adverse events (SAE) deemed related to treatment throughout the study period (Days 1-21 [1-33 for 5-dose intervention]), and at 30 days post-intervention (Day 49 [Day 61 for 5-dose intervention]).

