3.3.3 Discontinuation of medication

Participants who decide to discontinue study medication, but who do not withdraw their consent, will be withdrawn from the study, and will cease study tasks, although their existing data will be kept in the data set. These participants may be replaced.

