7.2.1 Enrollment and Baseline (Day 1)

Participants will be approached within 2-3 days of beginning residential treatment based on initial screening from EMR and enrolled into the study if they consent.

The following **standard of care data** will be collected from the EMR for research purposes:

- Demographic information (age, gender, race, contact information)
- Detailed medical history
- Physical examination
- Admission diagnoses

- Results from standard laboratory safety tests performed on admission (complete blood count, comprehensive metabolic panel)
- Current medication usage (concomitant medications)
- Results of urine pregnancy test at admission (if applicable)

The following **research-only activities** will be performed prior to randomization:

- A psychiatric assessment will be conducted:
 - o M.I.N.I. 7.0.2
 - o Form 90-DI
 - o HAM-D
 - o STAI-Y1
 - o C-SSRS
- Body weight will be measured
- 12-lead EKG will be performed
- Collection of stress response, sleep, and activity measurements will be initiated via actigraphy wristband (a "wearable" wristband).

Any participant that reports recent suicidal ideation or behavior on the screening C-SSRS will be referred for further immediate evaluation by a clinician. Clinical judgement and additional consult with the Caron Medical Director, study PI, and/or study staff will be used to further clarify if the subject is eligible to continue in the study.

Participant will receive the actigraphy wristband from a study coordinator. The study coordinator will instruct the subject on use of the actigraph.

Randomization: After obtaining written consent, subjects who fulfill study criteria will be randomized to either the liraglutide or placebo treatment arm of the study using an equal allocation ratio (1:1) permuted-block randomization.

The following **research-only activities** will occur after randomization and will serve as baseline values to compare with values obtained after study drug dosing:

- Cue-elicited drug craving will be evaluated using VAS.
- Neurophysiology measurements using fNIRS and VAS.
- Collection of ambient drug craving, mood, and sleep data will be initiated with EMA.
- Monitoring of body weight and cardiorespiratory function.
- Aes and concomitant medications will be documented.

Collection of blood pressure, heart rate and respiratory rate data will be initiated with cardiorespiratory testing performed by study staff.

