8.2 Sample size determination

This is an exploratory study to accumulate pilot data. The primary endpoint of this study is cue-elicited self-reported craving VAS scores. A sample size of N=20 per group will give 80% power to detect an effect size of 0.91 based on a two-sided two-sample t-test with a significance level of alpha=0.05. Accounting for an estimated 20% attrition rate, we plan to randomize a total of 20*2/0.8=50 patients in the study. To preserve statistical power, the sample will not be balanced with regard to MAT and non-MAT participants.

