Data reduction including derivation of summary features for continuously collected data (e.g., sleep data, physiological data) will be performed before formal statistical analysis. Descriptive analysis will be performed to explore distributions of data and identify potential outliers. Assumptions and goodness of fit of statistical models will be assessed. Missing data, including mobile and ambulatory attrition and drop-out will be examined to ensure the validity of statistical models used. Because ambulatory and mobile monitoring will continue during laboratory assessment days, correlation analyses will be used to confirm the agreement between corresponding measures from the two approaches; this will both speed harmonization for follow-up analyses, and provide additional validation of the measures used in the both cases.

The primary endpoints of the EMA assessment will be the rate of reduction of craving across the approximately 21 day study period in the treatment condition compared to the control condition while controlling for the traditional craving triggers of sleep, stress, hunger, affect, and pain and discomfort. Sleep and activity will be measured using a multimodal approach with self-report via the morning EMA survey and wearable actigraphy to measure and account for subjective biases in sleep timing. Craving reduction will be primarily measured using EMA assessment, and will be modeled using linear mixed models in the multilevel modeling (MLM) framework. In MLM, subject-specific random effects are combined with population-level fixed effects to account for variability both within each individual and between individuals in a manner that allows participants with incomplete data to be included in the model. Craving reduction will be modeled as an effect of time in treatment, and differences in rate of craving reduction will be tested as an interaction between treatment state and time. Drs. [name], [name], and [name] each have extensive experience analyzing similar data in the multilevel modeling framework.

For secondary safety outcomes, intensive longitudinal methods such as time-varying effect models will be used to assess for changes in continuously measured outcomes (e.g. blood pressure, heart rate, respiratory rate, body weight) to account for repeated measures. The proportion of participants experiencing AE and SAE will be compared between treatments using chi-square analysis.

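### Section 8.3 compares AE and SAE proportions with no allowance for time observed, although observation time varies through attrition and an optional extension; the bias is conditional and modest

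*Combined protocol and SAP*

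**What the plan says.** Section 8.3 gives AEs one sentence of analysis: "The proportion of participants experiencing AE and SAE will be compared between treatments using chi-square analysis". It names no denominator, no time at risk and no rule for participants who leave early.

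Section 1.3 defines the endpoint as "Frequency of adverse events (AE) and serious adverse events (SAE) deemed related to treatment throughout the study period (Days 1-21 [1-33 for 5-dose intervention", and the same sentence goes on to include 30 days post-intervention. Section 7.2 and the schedules also record AEs at the 30-day call, which reaches everyone who has not withdrawn consent. Section 9.1 sets a different window, from first dose to 24 hours after the last dose, and a different scope, since it takes all events whatever their relationship to treatment.

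Other passages make observed time unequal:
- Section 8.2 sizes the trial by "Accounting for an estimated 20% attrition rate".
- Under Section 3.3.3, a participant who stops study drug but does not withdraw consent "will be withdrawn from the study, and will cease study tasks". Sections 3.3.2 and 3.3.3 allow such participants to be replaced.
- Under Section 7.1, participants decide by Day 18 whether to move from the 3-dose to the 5-dose procedure. Dosing then runs over Days 2-31 (30 days) instead of Days 2-19 (18 days).

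**The concern.** A participant who leaves event-free after a few doses scores the same as one observed event-free to the end. A participant who extends has 12 more dosing days in which to become a case. Randomization balances neither, because both happen after it. If either differs by arm, the chi-square compares proportions accumulated over different lengths of time, and the arm with less observed time shows the lower proportion even when the true hazards are equal.

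Safety is one of the two objectives in Section 1.1, and Section 2.3 makes demonstrated safety a condition for the next trial. With about 25 per arm, readers will rely on the estimates more than on the test.

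**Working it through.** **The plan's own figures.** Section 8.2 says "A sample size of N=20 per group will give 80% power to detect an effect size of 0.91". Its test compares two means by t-test, two-sided at the 5% level. The exact noncentral-t calculation (df 38) gives 80.1%. Allowing for attrition, 20 × 2 / 0.8 = 50, and 1:1 allocation gives 25 per arm. All of this reproduces. The documents give no AE rate and do not split the 20% by arm, reason or timing, so those are assumptions below.

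**Set-up.** The hazard of a first AE is constant and the same in both arms. Let r be the risk over a completed 3-dose window. With the Section 9.1 window, observation is 18 + 1 = 19 days (3-dose) or 30 + 1 = 31 days (5-dose). Then λ = −ln(1 − r)/19. I take r = 5%, 20%, 50% and 70%.

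**1. Exits unrelated to AEs.** Exit times are uniform over the 18 dosing days, with observation to one day later. The AE risk among leavers is

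p_e = 1 − e^(−λ) × (1 − e^(−18λ))/(18λ).

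The arm proportion with exit share w is (1 − w)r + w·p_e, so the gap between arms is (difference in w) × (r − p_e).

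Example, r = 50%: λ = 0.693/19 = 0.0365 and p_e = 0.293. Exits of 32% give 0.68 × 0.50 + 0.32 × 0.293 = 43.4%. Exits of 8% give 0.92 × 0.50 + 0.08 × 0.293 = 48.3%. The gap is 0.24 × 0.207 = 5.0 points. The SE at 25 per arm is √(0.434 × 0.566/25 + 0.483 × 0.517/25) = 14.1 points, so the gap is 0.35 SE.

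| Exits by arm (20% overall) | r = 5% | 20% | 50% | 70% |
|---|---|---|---|---|
| 20% / 20% | 0.0 | 0.0 | 0.0 | 0.0 |
| 32% / 8% | 0.6 | 2.2 | 5.0 | 6.2 |
| 40% / 0% (extreme) | 0.9 | 3.6 | 8.3 | 10.4 |

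Entries are points by which the high-exit arm looks lower. The largest, 10.4 points, is 0.77 SE.

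**2. Uptake of the extension.** The risk over 31 days is r₅ = 1 − (1 − r)^(31/19). For r = 50%, r₅ = 67.7%. If 20% of one arm extend, its proportion is 0.8 × 0.50 + 0.2 × 0.677 = 53.5%. If 60% of the other extend, it is 0.4 × 0.50 + 0.6 × 0.677 = 60.6%. The gap is 7.1 points (0.51 SE). At r = 5%, 20% and 70% it is 1.2, 4.2 and 6.4 points.

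**3. What shrinks the exit gap (32% / 8%).**
- Counting the 30-day call, with the hazard continuing off drug and r now the risk over 48 days: 0.2 to 1.9 points.
- 80% of the hazard in the first 6 days: 1.0, 2.2 and 2.6 points at r = 20%, 50% and 70%.
- Every exit follows an AE (simulation, r = 50%): 50.1% versus 49.9%, no bias beyond simulation error.

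**4. Are events per person-day a safe substitute?** No.
- In the AE-driven simulation the high-exit arm has 15.92 days per participant against 18.23. Crude rates are 3.15 and 2.74 per 100 person-days despite equal hazards.
- Take 80% of the hazard in the first 6 of 18 days, with exits at day 6. Rates are proportional to (0.90 + 0.10 × 0.8)/(0.90 × 18 + 0.10 × 6) = 0.0583 for 10% exits and (0.70 + 0.30 × 0.8)/(0.70 × 18 + 0.30 × 6) = 0.0653 for 30%. That is a false 12% excess. At 5% / 35% it is 18%.

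Time to first AE with censoring avoids these problems. It compares participants still under observation on the same day, and a participant who leaves because of an AE has already contributed the event.

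**The case against.** A reader might infer that the arm with more early exits will look safer. The documents do not support that as a general result. The 20% is an overall sample-size allowance for the craving endpoint, and an equal split produces no between-arm bias. Section 3.3.2 lists AEs among the reasons for withdrawal, and Section 18.7 treats the vital-sign triggers as events needing medical attention. Such leavers probably already count as cases, so AE-driven exits on liraglutide would not favour the drug.

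Nor is it safe to read all of the expected leavers (20% of 50 = 10) as event-free, or Section 1.3's word frequency as a count of repeat events. Section 8.3 itself pairs frequencies with percentages for categorical variables, and participant-level incidence is a conventional summary.

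The 30-day call restores much of the lost follow-up. Section 10.0 says the common side effects fade over time, which argues against a constant hazard. Section 8.3 also promises to examine drop-out when checking model validity.

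Most of this stands and limits the size of the point. It does not remove it. The call helps only if its events count, and Section 9.1 conflicts with Sections 1.3 and 7.2 on that. Drop-out checks have no stated consequence for a chi-square on proportions. None of it addresses the extension, which is written into the design.

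**Conclusion.** The plan builds in unequal observation time and analyses AEs as if it were equal. The resulting bias is conditional: it needs event-free exits, or extension uptake, to differ by arm. Under equal constant hazards it is about 1 to 7 points for 20% versus 60% extending and about 0.6 to 6 points for 32% versus 8% exits. In every case computed for the crude proportion it is below one SE at 25 per arm. The AE risks, splits and exit timing are assumptions; only the overall 20%, the windows and the dosing days come from the documents.

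The matter is a possibly tilted safety estimate in a secondary endpoint of an exploratory pilot. It is not a false significant test, and the documents do not show that either arm will be favoured. It is a minor to moderate improvement worth making because it is cheap.

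**What to change.** In Section 8.3:
1. Analyse all participants who received at least one dose, including those withdrawn and those later replaced.
2. Reconcile Sections 1.3, 7.2 and 9.1 into one AE window, stating whether events at the 30-day call count and whether the comparison covers related events only or all events.
3. Beside the crude proportion, compare time to first AE over the common period, with early leavers censored at last observation or withdrawal treated as a competing event. Day 19 is the last dosing day that both procedures share. If Day 21 is used, note that the two procedures already differ on Days 20-21.
4. Tabulate days observed and exits by arm and reason, and report extension-period AEs separately.
5. Keep events per person-day as description only.

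The cost is some wording and a little more analysis, using the AE, dosing and withdrawal records already planned. The downsides are that censoring must be assumed non-informative and that SAE estimates will remain imprecise.

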7.2 Study Procedures

- Physical and Psychological Screening Procedures: The screening will include:
 - 12-lead electrocardiogram (EKG)
 - Urine pregnancy test if female with childbearing potential
 - Psychiatric assessment including: the M.I.N.I International Neuropsychiatric Interview (M.I.N.I. 7.0.2), Form 90-Drug Inventory (Form 90-DI), Hamilton Depression scale (HAM-D), State-Trait Anxiety Inventory (STAI-Y1), and Columbia Suicide Severity Rating Scale (C-SSRS)

The C-SSRS will be administrated by appropriately trained personnel. All C-SSRS scores will be reported to the Caron Treatment Center Medical Director of Research and the Director of Research. At risk participants will be immediately reported to the Directors of Research. Any participant that reports recent suicidal ideation or behavior on the screening C-SSRS will be referred for further immediate evaluation by a clinician. Clinical judgement and additional consult with the Caron Medical Director, study PI, and/or study staff will be used to further clarify if the subject is eligible to continue in the study. Participants not at risk will be reported weekly.

The Directors will refer the clinical decision to the psychology and medical team. If the patient is deemed to be suicidal, and is willing to get help, the psychology staff will utilize their typical protocol and resources to find placement in a local psychiatric facility (e.g., Philhaven, Lancaster Behavioral Health). The patient may be transported via ambulance or via Caron transportation (depending on how safe staff feels it is to transfer) to the facility for admission. In the case that the participant is uncooperative, Service Access and Management, Inc. (SAM) will be notified to assist with emergency planning. Any participant who develops active suicidal ideation with some intent to act with or without a specific plan will be discontinued from study treatment.

• **Body Weight:** Body weight will be measured daily throughout the study (Days 1-21 [Days 1-33 for 5-dose intervention]).

Blood glucose:

- Blood samples to assess changes in more long-term indices of glycemic control, such as hemoglobin A1c (HbA_{1c}) and fructosamine, will be collected prior to the first dose of study drug (Day 2) and at the end of the target dose (Day 19 [and additionally at Day 31 for 5-dose intervention]). Samples will be analyzed by Caron's clinical laboratory.

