The smartphones that will be used for EMA data collection will have an app (the Wear-IT app) that will be put on the study smartphone provided to the participant while they are in the study. This smartphone will have a security application installed that prevents user access to all other applications that are not associated with data collection. Smartphones will not be activated on a cellular network resulting in the disabling of voice, text, and internet functions. Research staff will use brief in-person meetings (every other day) as a means to ensure devices are being charged, build rapport, answer participant questions, monitor compliance, and to manually download data for backup storage for upload to a secure server, Virtual COLO, at University Park in State College. Participants will need to plug the phone in to charge each night.

 Physiological Wearables: A "wearable" wristband will be worn throughout the study (Days 1-21 [Days 1-33 for 5-dose intervention]) to monitor stress responses, including acute

changes that may be associated with the drug delivery via injection. Data collected include heart rate, actigraphy for sleep and activity measurement, and stress responses (including acute changes in these measures that may be associated with the drug delivery via injection). A body temperature compliance sensor will be used to validate that the device is being worn. So that participants do not have to charge the actigraphy wristband themselves, participants will have up to two actigraphy wristbands assigned to them, and they will be charged or, if necessary, swapped out at their check-in sessions. Participants may wear the actigraphy wristband while showering or swimming if they wish.

- Neurophysiology Lab Day Measures: Participants will be tested at baseline (Day 1) and at the end of the target dose (Day 19 [and additionally Day 31 for 5-dose intervention]) for cortical activity using Functional Near Infrared Spectroscopy (fNIRS) and VAS during:
 - Visual cue reactivity task to: (a) opioid cues; (b) non-opioid control cues; (c) natural reward cues (e.g., pleasant pictures of food, puppies, positive relationships, etc.) and (d) emotionally neutral stimuli (e.g., images of household objects)
 - The VAS measure of craving pre-post visual cue reactivity task
 - Balloon Analogue Risk Task (BART)

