8.3 Statistical methods

The primary aim is to test whether liraglutide reduces craving in patients recovering from OUD in residential treatment. Analysis of covariance (ANCOVA) will be used to compare liraglutide versus placebo treatment groups controlling for baseline values of craving. Linear mixed effects models for repeated measurements will also be used to evaluate the difference in changes in these primary outcomes between treatment groups. The baseline and post-treatment outcomes are treated as dependent variables in the mixed model. Subjects with missing values can be incorporated in the mixed model analysis when data are missing at random. The moderating effect will be assessed by adding the interaction term between moderator and treatment group in the models.

SAS (version 9.4) and R (version 3.2.5) software will be used for analyses with a significance level of 0.05. Summary statistics including means, medians, ranges, and standard deviations will be computed for each continuous variable and frequencies with percentages for categorical variables. Identified data outliers will be further examined to determine if they are data entry errors, in which case they will be modified when possible; otherwise, values will be kept for final analysis.

Primary outcomes to assess efficacy are: (1) cue-elicited drug craving rated on a 100-pt VAS; and (2) ambient drug craving, derived from EMA of daily craving throughout the study period. Data analyses for cue-elicited craving will consist of a 2×2 ANOVA with medication status (pre- vs post-medication) as a within-group variable and medication type (liraglutide vs placebo) as a between-group variable.

Secondary analyses of self-reported craving measures will evaluate the role of MAT, specifically BUP/NA, in these results.

EMA and Wearable Assessment: Ambient drug craving derived from the EMA will be analyzed as a multilevel model in the regression framework and will test effects of medication status within-person and medication type between-person. Secondary analyses of EMA will examine the effect of time (e.g. study day) to identify differences across condition in the rate of decline in craving across time.

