For exploratory outcomes, analysis of fNIRs-based neuroimaging will utilize a 2 (Medication Status) x 2 (Medication Type) ANOVA to evaluate the change in oxygenation in prefrontal cortex in response to opioid drug cues vs neutral cues, with a region of interest in left middle frontal gyrus. Analysis of safety outcomes from baseline to the end of target dose and to end of rebound follow-up will be analyzed using intensive longitudinal methods similar to the analysis of secondary outcomes. Changes in indices of glycemic control measured at baseline and at end of the target dose (e.g. HgA1c, fructosamine) will be calculated as deltas, with comparisons made between treatments using unpaired t-tests or Mann Whitney U tests as appropriate.

Interim Power Analysis: one or more interim power analyses may be conducted during the study to assess the effect size needed to observe a significant drug effect for primary, secondary, and/or exploratory endpoints based on the data collected at that time. These analyses would not bias type 1 error rates and the study team will use this information to determine whether and when to perform an interim data analysis to justify advancement to the second phase of the funding award (UH phase). In particular, the confidence intervals around the parameters representing the primary endpoint will be used as an approximation of the power available for our primary endpoints using the current data. This

will be weighed against the original proposed power and the PI's estimates of likely power after completion of the grant period to determine whether an interim analysis is warranted.

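### Section 8.3 analyses fNIRS and glycaemic outcomes as unadjusted change scores; ANCOVA on the baseline already collected could add precision at no cost, probably more for fNIRS than for the blood markers (low severity)

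*Combined protocol and SAP*

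**What the plan says.** Section 8.3 sets out two analyses without a baseline covariate. The fNIRS analysis "will utilize a 2 (Medication Status) x 2 (Medication Type) ANOVA to evaluate the change in oxygenation in prefrontal cortex", contrasting opioid with neutral cues in a left middle frontal gyrus region of interest. HbA1c and fructosamine changes "will be calculated as deltas, with comparisons made between treatments using unpaired t-tests or Mann Whitney U tests as appropriate".

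A pre-dose baseline exists for both. For fNIRS, section 7.2 states: "Participants will be tested at baseline (Day 1) and at the end of the target dose" (Day 19, and also Day 31 in the 5-dose schedule). Blood samples for the glycaemic markers "will be collected prior to the first dose of study drug (Day 2) and at the end of the target dose". The Day 1 fNIRS session follows randomisation (section 7.2.1), but dosing starts on Day 2, so the Day 1 value is a legitimate covariate.

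For craving, the same section names three methods:

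- ANCOVA: "Analysis of covariance (ANCOVA) will be used to compare liraglutide versus placebo treatment groups controlling for baseline values of craving".
- A mixed model: "Linear mixed effects models for repeated measurements will also be used to evaluate the difference in changes in these primary outcomes between treatment groups".
- For the cue-elicited endpoint, the same unadjusted layout as for fNIRS: "Data analyses for cue-elicited craving will consist of a 2×2 ANOVA with medication status (pre- vs post-medication) as a within-group variable".

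**The concern.** In a pre/post by arm ANOVA the treatment effect is the interaction, and that test is a comparison of mean change between arms. So fNIRS and, explicitly, the glycaemic markers are both analysed as change scores. A change score subtracts the whole baseline value, however weakly it predicts the follow-up value. ANCOVA subtracts only the part that predicts it. When the correlation between visits is low or moderate, the change score carries avoidable noise and over-corrects for any baseline difference that arises by chance.

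With about 20 evaluable participants per arm, chance differences at baseline are not small. Section 2.3 presents this pilot as the basis for deciding on a larger trial, so the precision of its estimates matters even where no formal power is claimed.

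**Working it through.** **The plan's own figure.** Section 8.2 states: "A sample size of N=20 per group will give 80% power to detect an effect size of 0.91" (two-sided t-test, alpha 0.05). Noncentral-t power at n = 20 per arm and d = 0.91 is 80.1%, and 40/0.8 = 50 randomised. The figure reproduces. It applies to cue-elicited craving; no power is stated for fNIRS or glycaemic outcomes.

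**Inputs.** N = 40 evaluable (section 8.2, assumed to apply to these outcomes too) and 1:1 allocation (section 7.4.3). Assumed: equal SD s at both visits, a linear relation, and r, which the documents do not give and which is varied below.

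**Step 1: equivalence.** In a generated data set with 20 per arm, the 2×2 interaction F was 5.4769 and the squared t on change scores was 5.4769.

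**Step 2: large-sample variance.** Per participant:

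- Change score: 2(1 − r)s²
- ANCOVA: (1 − r²)s²
- Ratio: (1 − r²) / [2(1 − r)] = (1 + r)/2

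If the SDs differ (s₁ at baseline, s₂ at follow-up), the change-score variance minus the ANCOVA variance is s₁² + s₂² − 2r·s₁s₂ − (1 − r²)s₂² = (s₁ − r·s₂)². This is never negative, so in large samples ANCOVA is never the less precise.

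**Step 3: small-sample cost.** Estimating the slope inflates the ANCOVA variance by 1 + 1/(N − 4) = 1 + 1/36 = 1.028, and one degree of freedom is lost (37 against 38).

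| r | (1 + r)/2 | × 1.028 | ANCOVA power if change score has 80% | Detectable difference at 80% power, in s: change → ANCOVA |
|---|---|---|---|---|
| 0.3 | 0.65 | 0.67 | 92.9% | 1.08 → 0.88 |
| 0.5 | 0.75 | 0.77 | 89.1% | 0.91 → 0.80 |
| 0.7 | 0.85 | 0.87 | 85.0% | 0.70 → 0.66 |
| 0.9 | 0.95 | 0.98 | 80.9% | 0.41 → 0.40 |
| 0.95 | 0.975 | 1.00 | 79.9% | 0.287 → 0.288 |
| 0.98 | 0.99 | 1.02 | 79.3% | 0.182 → 0.184 |

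Break-even is at r = 2/1.028 − 1, about 0.946. Simulation (20,000 trials per value) gave ratios of 0.666, 0.769, 0.924 and 1.001 at r = 0.3, 0.5, 0.8 and 0.95. The matching formula value at r = 0.8 is 0.90 × 1.028 = 0.925.

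**Step 4: chance imbalance.** The baseline difference between arms has standard error √(2/20) = 0.32 s. Given an imbalance of d, the change-score estimate moves by (1 − r)d in the opposite direction. For a one-standard-error imbalance that is 0.7 × 0.32 = 0.22 s at r = 0.3 and 0.5 × 0.32 = 0.16 s at r = 0.5. ANCOVA removes this shift.

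**The case against.** Much of the case on the other side is sound.

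- **Validity.** Under 1:1 randomisation the change-score comparison is unbiased over repeated randomisations. A reader might infer from regression to the mean that these tests are invalid. They are not; step 4 describes sensitivity to the imbalance in one realised trial, which is a matter of precision.
- **Size.** A reader might take a saving of roughly a third as established. The documents give no r for any of these outcomes. For HbA1c and fructosamine they point towards a high r: section 1.3 describes these measures as slow to change, over weeks to months, and the draws are 17 days apart. The gain there may be nil or very slightly negative.
- **Rank test.** The glycaemic plan also allows Mann-Whitney U, to which the variance ratio does not directly apply.
- **A settled craving method.** A reader might infer that ANCOVA is already the craving analysis and that fNIRS departs from it. Section 8.3 does not support that, because cue-elicited craving also receives the unadjusted 2×2 ANOVA.
- **Importance.** fNIRS is exploratory. Glycaemic control is listed as secondary in section 1.3 and exploratory in section 1.4. Change scores do match the endpoints as worded.

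These points limit the importance of the matter. None shows that the unadjusted analyses are as good as ANCOVA across the plausible range. The possible loss from switching is about 2% of variance at r = 0.98; the possible gain is 13% to 33% at r from 0.7 to 0.3.

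**Conclusion.** The point holds as a free improvement of low severity. Both analyses leave a collected baseline out of the model. Adjusting for it reduces the variance of the treatment effect by about 33% at r = 0.3, 23% at 0.5, 13% at 0.7 and 2% at 0.9, and by nothing from about 0.95. These figures rest on equal SDs, linearity, 20 evaluable per arm and an assumed r.

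The gain could be material for fNIRS, where nothing in the documents suggests a near-perfect correlation, and may be negligible for the glycaemic markers. It does not affect the sample size or the validity of the planned tests. The same reasoning covers the 2×2 ANOVA given to cue-elicited craving, the endpoint the trial is sized on, where section 8.3 is also inconsistent with its own ANCOVA statement.

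**What to change.** In section 8.3:

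1. Analyse Day 19 left middle frontal gyrus oxygenation (opioid minus neutral) by ANCOVA with arm as factor and the Day 1 value as covariate.
2. Analyse Day 19 HbA1c and fructosamine by ANCOVA with the Day 2 pre-dose value as covariate. Use a rank-based ANCOVA if residuals are clearly non-normal, in place of Mann-Whitney U on deltas.
3. Name Day 19 as the analysis visit, since section 7.2.5 schedules it for both intervention lengths. Analyse Day 31 data separately: a two-level time factor cannot hold a third visit, and section 7.1 makes the extension depend on availability and choice.
4. Replace the 2×2 ANOVA for cue-elicited craving with the same baseline-adjusted ANCOVA, so that it agrees with the ANCOVA statement at the start of the section.

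The cost is a wording change to the analysis plan, best made before unblinding. It needs no new data, visits or participants.
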